Inferences about a disease state from this study can be derived from several logical approaches. These approaches can be grouped into two categories: (1) those dealing with symptoms which can be used to construct a symptom complex that may represent disease, and (2) those dealing with physical signs which in themselves represent disease. In the former, one can form a subset of individuals that have symptoms (e.g., infertility) and study them during the morbidity and follow-up studies. Focusing on the overall patterns of alleged symptoms and categorizing them into a symptom complex may identify those individuals with a disease syndrome, or those at higher risk of developing disease (e.g., genetic disorders, cancer). In the latter approach, data on abnormal physical signs (e.g., genetic defects in offspring) and laboratory results can be compared between exposed and non-exposed groups in an attempt to again establish the presence or absence of disease. By putting this array of data into a logical decision-making scheme, specific relative risks can be calculated in the follow-up study.

FIGURE 5

CONTROL REPLACEMENT FOR THE MORBIDITY AND FOLLOW UP STUDIES

● QUESTIONNAIRE DATA

* LOSS TO STUDY

○ RECONSTRUCTED DATA

☆ PHYSICAL EXAMINATION DATA

By the use of combinational and correlational analyses, statements about the probability of a disease state, a subclinical state, and over-reporting bias can be attempted. If the development of symptoms in the exposed group is positively correlated with physical findings, and this correlation is absent in the control group, a statement concerning the existence of a possible disease state can be made. By taking these possible combinations of observations and viewing them in the context of associated positive verifiers, negative bias indicators, and positive exposure index, the probability of over-reporting bias acting in these circumstances can be substantially reduced and, as a result, any statement concerning the existence of disease is strengthened. Similarly, if symptoms in the exposed group do not correlate with the development of findings, but are associated with positive laboratory results, a statement concerning the existence of a subclinical disease state can be made. However, if comparisons within the RANCH HAND group reveal a negative correlation between reported symptoms and the presence of abnormal physical signs, then an over-reporting bias and/or subclinical disease state is suggested.

Another method to assist in the determination of a disease state is the use of normalized exposure index and the application of regression techniques to the resulting curve. If there is a positive correlation between increased exposure and the presence of various abnormal physical signs and/or verifiable symptoms, then a symptom complex or disease syndrome is suggested. Factors suspected of altering the classical dose-response curve include cellular repair mechanisms and the hypothesized release of TCDD from adipose tissue following weight loss. The addition of multivariate techniques to the regression analyses will strengthen statements about the presence of disease. Beyond these pair-wise and group comparisons, newer techniques of pattern recognition, such as Factor Analysis and Cluster Theory, are being considered in order to achieve a more automatic and objective analysis.

The strength of any inferences made from these analyses is dependent upon the statistical power inherent in the study. In addition, due to the possibility of latency being a factor in this study, a negative analysis at any time within the study does not categorically imply lack of disease, since sufficient time for emergence may not have passed.

G. Determinations of Exposure Indices:

(1) Exposure Concepts

A major concern in conducting this study is the lack of accurate exposure data. Although most personnel assigned to RANCH HAND squadrons were undoubtedly exposed to Herbicide Orange and TCDD, the exposures within the group must have varied widely. Exposure to herbicides and TCDD by RANCH HAND personnel occurred almost daily. Anecdotal information suggests that many had direct skin contact which was repetitive over a long period of time

(one-year tour for most individuals). Further, it is also suggested that most RANCH HAND personnel felt that the herbicides employed in the operations were not toxic to animals and man and hence, they did not exercise the caution in handling these chemicals that is recommended today. Several individuals have, in fact, repetitively tasted or drunk Herbicide Orange to convince their colleagues or the press of its safety.

From a historical review of RANCH HAND operations, most individuals can be classified into one of three groups based on their likely potential for exposure to the herbicides:

- | | |
|--|--------------------|
| (1) Pilots, Co-pilots and Navigators: | low potential |
| (2) Crew Chiefs, Aircraft Mechanic, and other Support Personnel: | moderate potential |
| (3) Console Operators and Flight Engineers: | high potential |

The "pilot" group probably received most of their exposure during pre-flight checks as well as during the actual dissemination missions. The crew chief group experienced contact with herbicides during dedrumming and aircraft loading operations as well as during on-site repair of the aircraft and spray equipment. The console operator group was exposed while supervising the loading of the aircraft, during ground testing the equipment, and by tank leakage during dissemination missions.

The available historical records on Operation RANCH HAND indicate that personnel assigned to the project seldom had a "routine" work schedule or environment, thus complicating estimates of the level of herbicide and dioxin exposure. Since actual exposure data (e.g., mg of herbicide/kg body wt) are not available, the establishment of an exposure index will be attempted. The exposure index will be calculated for each RANCH HAND individual to obtain a standardized frequency distribution. The exposure index will be calculated by evaluating the known factors that would have influenced exposure. For aircrew members, these will include such factors as:

- (1) Date of tour with RANCH HAND in Vietnam.
- (2) Number and lengths of tours in Vietnam with RANCH HAND.
- (3) Number of herbicide dissemination missions (as reflected by flying hours and air medals).
- (4) Herbicides employed (yearly records are available that reflect the amount of each herbicide sprayed).
- (5) Crew position.
- (6) Routes of exposure (the major route of exposure for most RANCH HAND personnel was probably percutaneous, although for the console operator, exposure through inhalation may have also been significant).

An exposure index may be derived from consideration of the above factors, i.e., it is a function of those factors:

$$E_I = f(D, T, P, C, R, H),$$

where E_I = Exposure Index

D = Dioxin Concentration Estimate During RANCH HAND Tour

The date of tour with RANCH HAND is important since mean dioxin concentrations in the herbicides changed by a factor of 16 between pre-1965 and post-1965. In 1965, both high and low dioxin formulations were available. Thus, a scale of values for TCDD are:

Pre-196532
196516
Post-19652

T = Duration of Exposure/Number of Missions Flown

P = Proportion of 2,4,5-T Herbicides Used

The ratio value of the amount of 2,4,5-T containing Herbicide applied for any given year against total amount of the herbicide applied during the same year. Data on herbicide expenditures by year are available. For example in 1962, Purple comprised 88 percent of all herbicides used that year, while in 1966, Herbicide Orange accounted for 66 percent of the total amount of herbicide applied.

C = Crew Position/AFSC

Relative exposure values for this factor will be determined by separate studies.

R = Route of Exposure

Relative values for exposures via ingestion, inhalation or percutaneous absorption will need to be evaluated from literature, computer modeling, and inflight determinations using a Herbicide Orange simulant.

H = Exposure History

A relative value based upon the subject's preception as to the magnitude of his own exposure. This will be obtained from the questionnaire and may reflect no exposure, a light exposure, a moderate exposure or a heavy exposure. A weighted value will be assigned to each exposure estimate, if possible.

(2) Proposed Studies

Within the exposure index equation, relative exposure values for two factors are lacking; crew position within the C-123 aircraft and the route of exposure. Approaches which will be used in obtaining estimates for these two factors include (1) use of a diffusion model which would consider the internal aircraft volume and configuration in computing specified source strengths and concentration levels; (2) use of quantitative data obtained at specified points within the aircraft following actual C-123A/A 45Y-1 dissemination missions using a Herbicide Orange Simulant; and (3) use of a combination of the above two methods. Discussion with personnel of the U.S. Army Environmental Hygiene Agency and the Chemical Systems Laboratory, Edgewood Area, Aberdeen Proving Grounds, Maryland, suggest that the dispersion of herbicide vapors and particles within the C-123 aircraft could be modeled provided data could be obtained for selected parameters. These parameters include:

- (1) Air flow measurements within the aircraft under flying conditions simulating those encountered during actual RANCH HAND missions.
- (2) Physical properties of Herbicide Orange components.
- (3) Internal volume of aircraft and individual compartments.
- (4) Temperatures of internal surfaces.
- (5) Estimate of surface area on the floor of the aircraft.

Given a specific scenario, for example, a 25 sq ft spill involving two gallons of Herbicide Orange on the aircraft floor during a mission, the model could determine the magnitude and duration of the chemical concentration in the areas near the console operator versus the air concentration in the cockpit. The key to determining the magnitude and route of exposure of C-123 aircrew members is obviously selecting the most likely aircraft configuration used during RANCH HAND and determining the frequency and magnitude of spills within the aircraft. These observations will come from the recollection of personal observations by RANCH HAND personnel.

The 355th TAS/Spray Branch, Rickenbacker AFB OH is presently using the C-123 aircraft configured with the A/A 45 Y-1 Internal Dispenser. Air flow measurements, volume determinations, and surface temperature data will be obtained for modeling and simulant studies. A suitable Herbicide Orange Simulant was developed by the USAF in 1965 and consisted of glycerine, water, and sodium thio-sulfate in a ratio of 68:16.8:15.2, respectively. Since physical and chemical data are available on the simulant, the addition of a sodium fluorescein tracer may permit particulate sizing and quantitative determinations of the extent of contamination in the air of the aircraft and on the surfaces of the aircraft and on aircrew members.

An estimate of relative exposure for non-flying personnel will be developed in a different manner. The Air Force conducted extensive industrial hygiene monitoring programs during the dedrumming and incineration of Herbicide Orange, Project PACER HO, (See Young, et al., 1978). These monitoring data (e.g., breathing zone data) and recently conducted, but as yet unpublished data on percutaneous absorption of 2,4,5-T in humans during actual spray operations in reforestation programs (Dow Chemical U.S.A., Midland MI, 1979), will permit more refined calculations of exposure estimates for this group of individuals. When these concepts are used to calculate an exposure estimate, there will be a group of RANCH HAND individuals with an exposure index of zero (clerical/administrative personnel with little or no flight line duties).

In the event that these more elaborate exposure index calculations are not feasible, two other approaches to the exposure estimate are available. A crude index can be constructed, based solely on the duration of RVN duty and the TCDD concentration of the herbicides used each year. While such an index would be less precise in defining an individual's estimated level of exposure, it would still permit valid comparisons within the RANCH HAND population. Stratification techniques could also be employed using AFSC and duration of exposure (RVN duty) as the grouping criteria.

VI. Statistical Methodology

A. Introduction

The design of the study is presented in schematic form in Figure 6. R' refers to the RANCH HAND personnel and C'' refers to the collection of all possible control individuals. As defined, R' and C'' will contain individuals who are deceased. Since C'' may be 15 to 25 times larger than R', a randomized subsample C' of C'' will be obtained. C' will be constructed from C'' by computer selection of the ten best matched controls for each exposed study subject. As previously noted, close matches will be made for the variables of age, AFSC, RVN tour length, and race. The matched controls will form ten cohorts, C₁ through C₁₀, as previously shown in Figure 1. A 50% random sample from each of the matched control sets of 10 will be selected for inclusion in the mortality assessment so that a group, C' is obtained that consists of 5 matched controls for each exposed subject. These controls will be designated as initial replacement candidates for the morbidity and followup studies. The remaining individuals in the control set will be additional replacement candidates in the event that replacement must occur beyond the members of the mortality set (see Figure 2). C' will be constructed without regard to whether the individual is currently living or dead so that an assessment of mortality can be accomplished.

Referring again to Figure 6, R and C indicate living RANCH HAND members and primary matched controls. If $m_{R'}$ is the proportion of R' found to be deceased, then,

$$R = (1 - m_{R'})R'$$

The questionnaire will provide data concerning specific symptoms and other findings in the R and C groups. Thus, various questionnaire finding rates in R, s_R , will be calculated and compared with the corresponding rates in C, s_C .

[figure not shown]
The questionnaire will allow allocation of RANCH HAND personnel into those with symptoms on questionnaire, indicated by RS, and those without, \overline{RS} . Similarly, the control individuals will be placed into symptomatic, indicated CS, and asymptomatic, \overline{CS} groups.

The physical examination performed on individuals from R and C will allow estimation and comparison of rates of physical findings in these groups. Rates of abnormal physical findings can be symbolically indicated as f_R and f_C for RANCH HAND and control groups respectively. Comparison of these rates is very important and details will be discussed below.

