Operation RANCH HAND personnel flew C-123 aircraft in RVN during 1962-1970. Data from hand-compiled lists obtained through the RANCH HAND Association (a reunion organization), Air Force personnel computer entries, historical records and actual C-123 flight orders, place the estimated study population at approximately 1200 individuals. Of those personnel confirmed by the USAF computer system, 25% are still on active duty, with the remainder being composed of retired or separated persons. An indepth search to identify all RANCH HAND participants is being conducted of all organizational records stored at the Military Records Division, National Personnel Records Center (NPRC), St. Louis, Missouri. Detailed advertisements in active/retired military trade journals, VA publications, and local newspapers may be pursued in the near future to insure maximal ascertainment/identification of the exposed group. Introductory letters will be sent to the last known address of all identified persons, and nonresponse will be pursued by cross-locator systems available within the government (e.g., Social Security Administration, VA, Internal Revenue Service). Significant efforts will be made to account for at least 99% of the total population (see Figure A-2, Section XII). Because of the limited number of estimated RANCH HAND personnel (1200), no subsampling of the exposed group is planned in any phase of the study. All members will be strongly encouraged to participate in all phases of the investigation.

(a) Known or Predicted Characteristics of the Exposed Group

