A review of all specialized flight units present during the RVN conflict, reveals clearly that there is no absolutely ideal control group for the RANCH HAND population. C-130 aircrew members and support personnel were selected because of sufficient population size, similar training profiles, and psychologic similarities to the RANCH HAND Group.

Total ascertainment of the C-130 population is being conducted by computer selection for specific military flying organizations, foreign country service and years of service. Over 2.3 million personnel records have already been scanned and the approximate C-130 sample size is 25,000 individuals. Aircrew members who flew C-130 aircraft in RVN during 1962-1970 will be selected as controls for the RANCH HAND aircrew population and the C-130 flight line maintenance population will be ascertained from personnel records by similar mechanisms, and will serve as the specific control population for the RANCH HAND support personnel. The proportions on active duty, and non-active duty status are expected to parallel the patterns in the exposed group.

Another possible control group, the non-RANCH HAND C-123 population, is known to be too small (approximately 3000) to provide adequate sampling flexibility and replacement under the proposed matched variable concept (see below and Section VI, I). Many of the RANCH HAND aircraft were reconfigured for transport and insecticide missions and thus, non-RANCH HAND crews responsible for these other missions, may have been exposed to significant Herbicide Orange residues in these aircraft.

Therefore, this group may not have been truly unexposed to herbicides, and was discarded as an appropriate control population. Crewmembers of C-7 transport aircraft were also considered as a potential control group; however, because of small size (1000-1200) and the fact that they served in RVN only during the post 1967 era, they were also dropped from consideration.

(a) Known or Predicted Characteristics of the Control Group

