KNOWN FACTORS	STUDY GROUP		POSSIBLE CONTROL GROUPS	
	RANCH HAND C-123	Non-RANCH HAND C-123	C-7	C-130
POPULATION SIZE	1200	3000	1200	25,000
OFFICER/ENLISTED RATIO	1:2	1:2	1:2	1:2
AIRCRAFT FUEL (AV-GAS)	YES (+JP-4)*	YES (+JP-4)*	YES	NO (JP-4 only)
OCCUPATIONAL HERBICIDE EXPOSURE	YES	YES/NO**	NO	NO
ESTIMATED FACTORS				
OCCUPATIONAL INSECTICIDE EXPOSURE	2+	1+ to 4+	0	0
COMBAT HAZARD	4+	3+	3+	2+
RVN-IN COUNTRY ASSIGNMENT	4+	4+	4+	2+

*In 1968, aircraft were modified with a JP-4 booster.

**Contaminated aircraft reconfigured for transport may have resulted in exposure to non-RANCH HAND personnel.

variables is as follows: (1) many clinical symptoms and signs allegedly attributed to herbicide exposure (see literature review) can also be attributed to an aging effect, or to collateral diseases more commonly associated with advancing age, (2) AFSC controls specifically for officer-enlisted status (as well as crewmember or noncrewmember status), a variable strongly linked to educational background, current socio-economic status, and moderately linked to age (5 year median difference) and socio-economic background, (3) total length of tour in RVN (measured in six month intervals, or actual flying hours, if feasible) will control for the generalized probability of combat morbidity, mortality, and for combat induced neuro-psychiatric disorders; additionally, length of tour may reflect effects related to intensity of alcohol consumption, drug consumption (chemoprophylactic or illicit), and degree of tropical disease acquisition and (4) race controls for differences in chronic disease development, socio-economic background, etc. (note: there is possible racial discordance for VA claimants).

(5) Study Group Selection Procedures

(a) Mortality Analysis

For the mortality analysis, ten controls will be selected for each exposed subject, regardless of current vital status (Figure 1). The control individuals will be randomly assigned to one of 10 cohorts, C₁ through C₁₀. All of the exposed individuals and a 50% random sample of each set of controls will be included in the mortality analysis. The current vital status of each exposed-control set will be determined, and their mortality experience will be followed throughout the duration of this study. In addition to providing a 1:5 mortality analysis, this technique will characterize the mortality experience of each control cohort.

[figure not shown]

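### Exposed men can enter the cohort by routes open only to the living while controls enter regardless of vital status, so the past-mortality SMR can be biased downward

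*Protocol*

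**What the plan says.** **Exposed group.** Section V.B(1) bases its estimate of about 1200 men on these sources: "Data from hand-compiled lists obtained through the RANCH HAND Association (a reunion organization), Air Force personnel computer entries, historical records and actual C-123 flight orders". It continues: "An indepth search to identify all RANCH HAND participants is being conducted of all organizational records stored at the Military Records Division". It then adds a conditional route, meant to make identification as complete as possible: "Detailed advertisements in active/retired military trade journals, VA publications, and local newspapers may be pursued". Section VI.A states that the exposed cohort R' includes deceased men.

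**Control group.** Section V.B(3) says: "Total ascertainment of the C-130 population is being conducted by computer selection for specific military flying organizations, foreign country service and years of service". No association or advertisement route is described. For the mortality analysis, section V.B(5)(a) says that "ten controls will be selected for each exposed subject, regardless of current vital status".

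**Where exposed records may fail.** Section V.B(1)(a) concedes that men who did flight-line maintenance in 1965 may not be adequately identifiable. Table 5 marks primary maintenance personnel for August 1964 to December 1966 as Yes/No, with a footnote that Morning Reports may close the gap.

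**Bias already recognised.** Section VIII.B (Group Accountability Bias) expects RANCH HAND deaths to be better reported than control deaths, which would create an apparent exposed excess. Its remedy is to keep unaccounted subjects below 1% in both groups.

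The protocol describes no flag for how an exposed man was identified and no analysis limited to men identified from records.

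**The concern.** The two cohorts are listed by different rules. A control is listed because a service record names him. An exposed man may be listed for the same reason, or because he was alive to answer a notice. For the second kind of man, entry depends on the outcome that the review of past mortality measures. Dead men from the same units whom the records also miss are never listed, so they cannot be counted.

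The stated safeguards act at a later stage. The 99% accounting target in V.B(1) and the 1% limit in VIII.B concern tracing men already on the list. The check of tour data against personnel records in section XIII verifies a man who has been contacted; it does not recover a dead man who was never listed.

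Two results are at stake. The first is the past-mortality SMR of section VI.C, where a real excess could be diluted. The second is the regression of mortality on the exposure index (VI.H). Section V.G scales dioxin at 32 before 1965, 16 in 1965 and 2 afterwards, so part of the window with doubtful records is a high-dioxin period.

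**Working it through.** **The protocol's own ascertainment figure.** Section VI.C says that 1% unaccounted can alter a mortality rate of 0.10 by as much as 10%. This reproduces: 0.01 / 0.10 = 10%. The protocol gives no figure for bias in who enters the exposed cohort.

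**Inputs.** Control mortality 0.10 (the example in VI.C); about 1200 exposed men (V.B(1)); five mortality controls each, so 6000 (V.B(5)(a)). Assumed: q, the share of R' that enters solely by a living-only route; a true SMR of 130 for the power illustration; two-sided alpha 0.05.

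**Past mortality.** These men have no past deaths, and the others die at the true rate, so

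observed ratio = true ratio × (1 - q).

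This takes expected deaths per man to be the same in both kinds of exposed man.

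**Power for a true SMR of 130.** Exposed deaths d1 = 1200 × (1 - q) × 0.10 × 1.3; control deaths d2 = 6000 × 0.10 = 600; SE = √(1/d1 + 1/d2); power = Φ(ln[1.3(1 - q)] / SE - 1.96). At q = 0: d1 = 156, SE = 0.0899, ln 1.3 = 0.2624, so Φ(0.96) = 0.83. At q = 1%: d1 = 154.4, SE = 0.0902, ln 1.287 = 0.2523, so Φ(0.84) = 0.80.

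| q | SMR if truth is 100 | Power if truth is 130 |
|---|---|---|
| 0 | 100 | 0.83 |
| 1% | 99 | 0.80 |
| 5% | 95 | 0.63 |
| 10% | 90 | 0.39 |
| 20% | 80 | 0.06 |

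An unmatched two-proportion calculation with 1000 exposed and 5000 controls (section VI.B puts R' at about 1000) gives 0.79, 0.76, 0.60, 0.37 and 0.06 for the same values of q.

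**The opposing bias of VIII.B.** If deaths equal to a fraction u of controls are missed and no exposed deaths are, the ratio is multiplied by 0.10 / (0.10 - u): 1.11 at u = 1% and 1.43 at u = 3%, the range tolerated in VI.C. Combined with u = 1%, the net factor (1 - q) × 0.10 / 0.09 is 1.06 at q = 5%, 1.00 at q = 10% and 0.89 at q = 20%. The sign therefore depends on two unknowns.

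**Morbidity.** If men found only by other routes have k times the prevalence of the rest, the exposed rate is multiplied by 1 - q + qk. With k = 2 this is 1.05 at q = 5% and 1.10 at q = 10%; with k = 0.5 it is 0.975 and 0.95. The protocol gives no basis for k.

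**The case against.** **Advertisements are only a possible supplement.** The main sources are flight orders, personnel entries, historical records and the organizational records search, all of which can list dead men. The Executive Summary expects total ascertainment, and nothing says that any man will be found solely by a notice. This stands: q may be zero or very small, and at 1% the effect is slight. The 20% row would need 240 of 1200 men to be missing from every service record.

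**The association lists are not shown to omit the dead.** This also stands. Section VIII.B expects the association to improve the reporting of deaths. The certain living-only route is the advertisement; the lists matter only so far as they miss men who had died.

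**The protocol already sets aside groups that records cannot define.** Drum handlers and similar groups are analysed separately under V.B(2), and maintenance men must have been directly assigned to RANCH HAND. This helps in part. Table 5 still leaves primary maintenance for August 1964 to December 1966 uncertain, and men found for that window would be pooled into the main cohort.

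**A flag and a sensitivity analysis could sit in an analysis plan.** Perhaps so, but who belongs to R' is fixed by the protocol, and identification was already under way.

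**Stronger reading.** A reader might infer that RANCH HAND mortality will come out too low and morbidity too high. The documents do not support that. The mortality effect concerns deaths before enrolment, not those that accrue later, and VIII.B describes a bias in the other direction. For morbidity, section VIII.D lists pressures toward under-reporting (loyalty, career fears) as well as over-reporting (compensation, publicity).

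**Conclusion.** The point holds as a conditional risk. The protocol admits an entry route to the exposed cohort that requires survival, has no such route for controls, and discusses only the opposite mortality bias. The past-mortality SMR can be multiplied by about (1 - q): 0.99, 0.95 and 0.90 at q = 1%, 5% and 10%. These values of q are assumptions, the 10% mortality is the protocol's example, and the bias vanishes if every man is found from records. The most plausible place for it is the August 1964 to December 1966 flight-line maintenance group. Net mortality bias could go either way, and two opposed biases of unknown size cannot be assumed to cancel. Upward morbidity bias from self-selected responders is possible but not demonstrated. The change is worth making because it is cheap while the lists are being built and hard to reconstruct after they are merged.

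**What to change.** 1. For the main mortality and morbidity comparisons, define R' as men identified or confirmable through a search of service-time records (flight orders, unit records, Morning Reports, personnel files) that is run independently of vital status, association lists and advertisements. A look-up prompted only by a living man's reply is not enough, since it leaves his dead counterparts unsearched.
2. Record each man's source of first identification and whether the independent search also found him.
3. Report the main results with and without men found only by other routes, and state how many there are, so that q is known.

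Section VI.I already treats replacement controls in this way, by flagging them and analysing the pairs with and without them.

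The cost is one source field, one extra analysis and possibly a slightly smaller main cohort.
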